## 16.4 Immunogenicity

*Analysis Sets: Immunogenicity analysis set*

### 16.4.1 Antidrug Antibody

The ADA results will be derived for each visit based on the algorithm in Table 9.

**Table 9** Algorithm for the Derivation of ADA Results

Sample Screen Result	Confirmatory	Titer	ADA Result
Negative	NA	NA	Negative
NR	NA	NA	NR
Positive	Negative	NA	Negative
Positive	NR	NA	NR
Positive	Positive	Number	Number
Positive	Positive	NR	Positive-TNR

NR = no result, NA = not applicable, TNR = titer no result.

Note that samples collected during and after the on-treatment period (e.g. safety follow-up) including the ones collected during the re-initiation period will be included in the analysis. Negative, number, or positive-TNR are valid results while number and positive-TNR are considered as positive. Participants will be characterized into different categories based on the criteria in Table 10.

**Table 10** Participants Characterized based on ADA Results

Category	Definition	Participant at Risk (Denominator for Incidence)
Never positive	No positive results at any time point	Number of participants with at least one valid result at any time point
Ever positive	At least one positive result at any time point, including baseline	Number of participants with at least one valid result at any time point
Pre-existing	A positive ADA result prior to treatment with bintrafusp alfa	Number of participants with valid baseline result
Treatment boosted	A positive ADA result prior to treatment with bintrafusp alfa and the titer $\geq 8^*$ baseline titer at least one post-baseline value	Number of participants with valid baseline result and at least one valid post-baseline result
Treatment emergent	Not positive prior to treatment with bintrafusp alfa and with at least one positive post-baseline result	Number of participants with at least one valid post-baseline result and without positive baseline result (including missing, NR)
Transient positive	If treatment emergent participants have - a single positive evaluation or - duration between first and last positive result $<16$ weeks and last assessment not positive	Number of participants with at least one valid post-baseline result and without positive baseline result (including missing, NR)
Persistent positive	If treatment emergent participants have duration between first and last positive result $\geq 16$ weeks or a positive evaluation at the last assessment	Number of participants with at least one valid post-baseline result and without positive baseline result (including missing, NR)

### Start of Immunogenicity Response

For participants with any positive ADA response, the date of the first assessment with positive ADA result will be considered as start date of ADA response.

Time to onset (weeks) of ADA response will be calculated as:

$$(\text{Date of first positive ADA assessment} - \text{start date of bintrafusp alfa treatment} + 1) / 7$$

Note: If the first positive is prior to the start of treatment, the formula is revised to:

$$(\text{Date of first positive ADA assessment} - \text{start date of bintrafusp alfa treatment}) / 7$$

### Duration of Immunogenicity Response

Duration of ADA immunogenicity response (weeks) is defined as:

$$(\text{Date of last positive ADA assessment} - \text{date of first positive ADA assessment} + 1) / 7$$

For participants with pre-existing positive, duration will be calculated from start date of bintrafusp alfa treatment rather than from date of first positive assessment. Participants still on treatment at the data cut-off and positive assessment at their last assessment before cut-off will be censored at the date of last assessment.

The following analysis will be described:

- The frequency and percentage of each ADA category will be tabulated
- The ADA titer value by timepoint will be summarized
- The maximum observed ADA titer per participant will be tabulated. For each discrete titer value, percentages will be calculated using the total number of participants in each ADA status group as the denominator
- The time to first ADA positive response will be summarized
- The duration of ADA immunogenicity response will be summarized.

The ADA category, titer, maximum titer, time to first ADA positive response and duration of response analyses will also be performed by subgroup:

- Japanese, non Japanese Asian, all Asian, non-Asian.

The following further analyses will also be described:

- Evaluation of potential effect of ADA on bintrafusp alfa safety (see section 15.1.1)
- Evaluation of potential effect of ADA on bintrafusp alfa efficacy
  - for best overall response according to RECIST 1.1 as adjudicated by IRC (see section 14.1.1)
  - for progression-free survival according to RECIST 1.1 as adjudicated by IRC (see section 14.4.2)
  - for duration of confirmed response according to RECIST 1.1 as adjudicated by IRC (see section 14.5.1)
  - for durable confirmed response according to RECIST 1.1 as adjudicated by IRC (see section 14.6.1)
  - for overall survival (see section 14.8.1)
- Evaluation of potential effect of ADA on bintrafusp alfa Pharmacokinetic (see section 16.1.2)

Potential effect of ADA on safety, efficacy and PK will be evaluated on ADA positive status (ever positive, never positive).

Listings of ADA results from ever positive participants will be provided with the following: participant ID, age, sex, race, ADA categories status, visit, date of assessment and results of screening, confirmatory and titer values. A further listing will contain: participant ID, age, sex, race, date of first ADA positive result, responder per IRC/investigator, date of response and timing of response related to the date of first ADA positive result. Responders will be defined as participants meeting confirmed CR or PR and non-responders as all other participants.

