 ADA=antidrug antibody, AE=adverse events, aPTT= activated partial thromboplastin time, β-HCG=β-human chorionic gonadotropin, CCI item module, BTC=biliary tract cancer, CCI, CR=complete response, CT=computed tomography, D=Day, ECG=electrocardiogram, ECOG PS=Eastern Cooperative Oncology Group performance status, CCI, CCI, HBV=hepatitis B virus, HCC-18=Hepatobiliary Cancer 18 item module, HCV=hepatitis C virus, HIV=human immunodeficiency virus, IDMC=Independent Data Monitoring Committee, INR=international normalized ratio, IRC=Independent review committee, IV=intravenous, MRI=magnetic resonance imaging, CCI, PD=progression of disease, PD-L1=programmed death ligand 1, PGIS=patient global impression of severity, PK=pharmacokinetics, PR=partial response, CCI, Q1W=every 1 week, Q2W=every 2 weeks, Q4W=every 4 weeks, Q6W=every 6 weeks, Q12W=every 12 weeks, SAE=serious adverse event, SP-A=Surfactant protein A, SP-D=Surfactant protein D, SpO2=blood oxygen saturation, T4=thyroxine, CCI, TSH=thyroid-stimulating hormone, V=visit, W=Week, W1D1=Week 1 Day 1.																

Table 2 M7824 Pharmacokinetic, Immunogenicity Sampling

M7824 Measure	Screening / Baseline Assessments	Treatment Phase ( $\pm$ 3 days)						End-of-Treatment Visit	Safety Follow-up Visit	Notes			
		V1	V2	V3	V4	V7	Until Progression Pre-infusion						
		W1	W3	W5	W7	W13							
Day -28 to First Treatment	D1 Pre/End Infusion	D15 Pre/End Infusion	D29 Pre/End Infusion	D43 Pre/End Infusion	D85 Pre/End Infusion	On the Day of or Within 7 Days of Decision	Up to 28 Days ( $\pm$ 5 days) After Last Treatment	12 Weeks ( $\pm$ 2 weeks) After Last Treatment					
Blood sample for PK		X/X	X/-	X/X	X/-	X/-	Q6W up to/including W25, then Q12W	X	X	Samples for PK analysis to be taken before (pre) infusion (as close to the start of the infusion as possible), immediately after the completion of infusion (as close to the completion as possible but no later than 30 minutes post end of infusion). The pre-dose sample should still be drawn even if dosing is ultimately deferred at the study visit. The exact time of each draw must be recorded. A protocol deviation will be defined by a sample not being drawn or time not being recorded.			
Blood sample for ADA	X		X/-	X/-	X/-	X/-	Q6W up to/including W25, then Q12W	X	X	Pre-dose ADA samples to be collected within 2 hours prior to study intervention infusions as scheduled.			

ADA=antidrug antibody, D=days, PK=pharmacokinetics, Q6W=every 6 weeks, Q12W=every 12 weeks; V=visit, W=Week.

## 2

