M7824 has shown promising clinical efficacy signal in BTC patients progressing after platinum-based 1L treatment (Study MS200647-0008). Thirty Asian participants were treated with M7824 at dose of 1200 mg every 2 weeks. As of 20 March 2018, 30 participants who had previously received 1L treatment for BTC, received M7824 for a median duration of 8.9 weeks (range: 2 to 57.6 weeks); 5 participants remained on treatment at the time of data cutoff. Seven participants had a confirmed objective response (OR) by Investigator read (ORR 23.3%) and 6 participants had a confirmed OR by IRC (ORR 20%), including 1 confirmation of response after cutoff. Per anatomical location, the ORR was 14.3% (1 out of 7) in study participants with extrahepatic CCA and 40% (4 out of 10) in study participants with intrahepatic CCA, 16.6% (2 out of 12) in study participants with gallbladder carcinoma. No responses were observed in ampullary cancer (0 out of 1). With a minimum follow-up of 8 months, the duration of response (DOR) ranged from 0.7 to 6.9 months with 5 of 7 responses ongoing at the data cutoff date. Besides the confirmed ORR, 1 additional participant had an ongoing partial response (PR) for 7.6+ months after initial progression. The observed clinical efficacy, therefore, compares favorably to the calculated benchmark of existing 2L treatment options and there is a strong rationale with preclinical and clinical data to justify further clinical development of M7824 in 2L BTC, with the potential to establish M7824 as the standard of care.

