### **Presentation of continuous and qualitative variables:**

Continuous (non-PK) variables will be summarized using descriptive statistics i.e.:

- Number of participants (N), number of participants with missing values
- Mean, standard deviation
- Median, 25th Percentile - 75th Percentile (Q1-Q3),
- Minimum, and maximum,

If there are no missing values, the number of participants with missing values should be set to 0.

Pharmacokinetic variables (concentrations and parameters) will be summarized as described in Section 16.1.2.

Qualitative variables will be summarized by counts and percentages.

Unless otherwise stated, the calculation of proportions will be based on the number of participants of the analysis set of interest. Therefore, counts of missing observations will be included in the denominator and presented as a separate category.

In case the analysis refers only to certain visits, percentages will be based on the number of participants still present in the study at that visit, unless otherwise specified.

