- The frequency and percentage of each nAb category will be tabulated for each assay individually and combined (either assay).
- The nAb titer value by timepoint will be summarized, per assay
- The maximum observed nAb titer per participant per assay will be tabulated. For each discrete titer value, percentages will be calculated using the total number of participants in each nAb status group as the denominator
- The time to first nAb positive response will be summarized, per assay
- The duration of nAb response will be summarized, per assay.

See Section 16.4.1 for the derivation of time to first positive response and duration of response.

The nAb category, titer, maximum titer, time to first nAb positive response and duration of response analyses will also be performed by subgroup:

- Japanese, non Japanese Asian, all Asian, non-Asian.

A listing of nAb results from ever positive participants (in either assay) will be provided with the following: participant ID, age, sex, race, nAb categories status, visit, date of assessment and results of screening and titer values. A further listing will contain: participant ID, age, sex, race, date of first nAb positive result, responder per IRC/investigator, date of response and timing of response related to the date of first nAb positive result. Responders will be defined as participants meeting confirmed CR or PR and non-responders as all other participants.

The following further analyses will also be described as follows:

- Evaluation of potential effect of nAb on bintrafusp alfa safety (see section 15.1.1)
- Evaluation of potential effect of nAb on bintrafusp alfa efficacy
  - for best overall response according to RECIST 1.1 as adjudicated by IRC (see section 14.1.1)
  - for progression-free survival according to RECIST 1.1 as adjudicated by IRC (see section 14.4.2)
  - for duration of confirmed response according to RECIST 1.1 as adjudicated by IRC (see section 14.5.1)
  - for durable confirmed response according to RECIST 1.1 as adjudicated by IRC (see section 14.6.1)
  - for overall survival (see section 14.8.1)
- Evaluation of potential effect of nAb on bintrafusp alfa Pharmacokinetic (see section 16.1.2)

Potential effect of nAb on safety, efficacy and PK will be evaluated on nAb positive status (ever positive in either assay, never positive).

CCI

CCI

## 17

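### ADA and nAb duration: participants positive only at a screening sample two or more days before first dose get a negative value, and off-treatment participants still positive at their last sample are counted as ended

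*SAP*

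**What the plan says.** The base formula stands in SAP 16.4.1, Duration of Immunogenicity Response, introduced by "Duration of ADA immunogenicity response (weeks) is defined as". It takes the date of the last positive ADA sample, subtracts the date of the first, adds one day and divides by 7. Two rules follow:

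- Start date: "For participants with pre-existing positive, duration will be calculated from start date of bintrafusp alfa treatment rather than from date of first positive assessment".
- Censoring: "Participants still on treatment at the data cut-off and positive assessment at their last assessment before cut-off will be censored" at the date of that last assessment.

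The output is stated only as "The duration of ADA immunogenicity response will be summarized", overall and for Japanese, non-Japanese Asian, all Asian and non-Asian participants. No time-to-event method is named. The SAP's general rule in Section 9 is "Continuous (non-PK) variables will be summarized using descriptive statistics i.e", followed by counts, mean, median, quartiles and range.

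For neutralizing antibodies, SAP 16.4.2 states "The duration of nAb response will be summarized, per assay" and refers back to 16.4.1 for the derivation.

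**The concern.** The start-date rule moves the start of the clock for pre-existing positives but leaves its end, the last positive sample, where it was. If the only positive sample was taken before first dose, the end precedes the start. SAP 16.4.1 deals with pre-dose positives one paragraph earlier: the time-to-onset formula under Start of Immunogenicity Response has a separate version for them. The duration formula has no counterpart.

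The censoring rule needs two conditions together: still on treatment at cut-off, and positive at the last assessment. Whether the end of a response was observed depends only on the second. A participant who has stopped treatment and is positive at the final sample has an end date just as unknown, yet enters the summary as a completed response.

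At stake is how the duration table reads. Characterizing immunogenicity is a secondary objective, and the table could show impossible values next to truncated ones without distinguishing either from observed durations.

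**Working it through.** The documents give no ADA or nAb duration figure, so there is none to reproduce. The check applies the written rules to cases.

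**Part 1: positive at screening only**

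Inputs:
- Pre-existing requires only a positive result before treatment (SAP Table 10).
- The baseline ADA sample falls in the window from Day -28 to first treatment. As Table 2 in Protocol Section 1.3 reads, there is no Day 1 ADA sample and the next is on Day 15.
- There is no Day 0 (SAP Section 9, Treatment day), so Day -d lies d days before first dose.

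Formula: duration = (last positive date - first dose date + 1)/7 = (-d + 1)/7 weeks.

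| Only positive sample | Calculation | Weeks |
|---|---|---|
| Day -28 | (-28 + 1)/7 | -3.86 |
| Day -14 | (-14 + 1)/7 | -1.86 |
| Day -7 | (-7 + 1)/7 | -0.86 |
| Day -2 | (-2 + 1)/7 | -0.14 |
| Day -1 | (-1 + 1)/7 | 0 |
| Day 1, pre-dose | (0 + 1)/7 | 0.14 |

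The base formula, first to last positive, would give 1/7 = 0.14 weeks in every row. The negative values come from the start-date rule alone.

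**Part 2: positive at the last sample, off treatment**

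Take a treatment-emergent participant whose first positive sample and last dose are both on Day 43, and whose last available sample is the 28-day follow-up on Day 43 + 28 = Day 71, still positive.

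- Duration: (71 - 43 + 1)/7 = 29/7 = 4.14 weeks, treated as completed.
- Category in Table 10: persistent positive, because the last assessment is positive. Treatment status plays no part. Table 12 has the same rule for nAb.
- The same sample results in someone still on treatment at cut-off would be censored at 4.14 weeks.

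With a longer series (first positive Day 15, last dose Day 57, still positive at 12 weeks on Day 57 + 84 = Day 141), the rule gives (141 - 15 + 1)/7 = 18.1 weeks as complete. The true value is at least 18.1 weeks. SAP 16.4.1 includes samples taken after the on-treatment period, so such cases can arise.

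**Direction of the effect**

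Counting a response as ended at a date when it was still present can only lower the estimated duration relative to censoring it there. An illustration used assumed inputs: exponential treatment time with the 8.9-week median from Protocol 2.2, onset uniform over weeks 0 to 8, cut-off 39 to 82 weeks after first dose, samples through 12 weeks after last dose, and exponential true duration.

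| Assumed mean true duration (weeks) | Last sample positive | Median as written | Median, all such participants censored | True median from first positive sample |
|---|---|---|---|---|
| 13 | 34% | 4.1 | 6.1 | 9.0 |
| 26 | 56% | 8.1 | 18.1 | 18.2 |
| 52 | 74% | 11.1 | 52.1 | 36.3 |

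In the first row part of the shortfall remains after censoring: ending a response at the last positive sample, rather than at the next negative, also shortens it. In the last row the repaired estimate overshoots, because it sits in the sparse tail. These runs support a direction, not a size.

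**The case against.** The strongest reply is that the SAP defines duration as the span between first and last positive samples and never claims to estimate true persistence. Persistence is reported through the categories in Tables 10 and 12, and the listings of ever-positive participants would expose a screening-only positive. This narrows the point without removing it. A negative span is wrong under any definition, and by censoring some participants the SAP itself treats duration as something that can outlast observation.

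A reader might infer that most responses would be cut short, or that medians would be roughly halved. The documents do not support that:

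- They give no ADA rate, no pre-existing rate and no onset pattern.
- The end of sampling matters. The endpoint in SAP Table 1 runs through 12 weeks after last treatment, but the ADA row of Protocol Table 2, as extracted, does not show clearly which follow-up visits are sampled. With exponential onset (mean 8 weeks) and true median durations of 12 or 26 weeks, the share positive at the last sample is about 60% or 76% if sampling stops at 4 weeks, and about 47% or 68% if it stops at 12.
- The exponential treatment-time assumption has a thin tail. In the Phase Ib study "5 participants remained on treatment at the time of data cutoff", which is 5/30 = 17% with at least 8 months of follow-up. The assumption leaves about 0.5^(34.8/8.9) = 6.7% at 8 months (34.8 weeks). A heavier tail lets the written rule censor more participants.

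Two further inferences also go too far. Not every screening-only positive gets a negative value: Day -1 gives 0 and a pre-dose Day 1 sample gives 0.14. And nothing shows that treatment length differs between the race subgroups, so a distorted comparison between them is possible but not established. Finally, negative results between two positives count as positive time, a smaller effect that lengthens duration.

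**Conclusion.** The concern stands on both parts, within limits. As written, the rule returns a negative duration for any participant whose sole positive is on Day -2 or earlier, down to -3.86 weeks at Day -28. It also counts an off-treatment participant who is positive at the last valid sample as having a completed response, which lowers duration as a measure of persistence and is out of line with Tables 10 and 12. Both carry over to nAb.

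The part 1 values are exact consequences of the SAP formula and the screening window. For part 2 only the downward direction can be claimed. The number of participants affected is unknown.

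The consequence is limited to the descriptive duration summaries and their race subgroups. The test of objective response rate, the ADA and nAb category counts, and the ever-positive versus never-positive comparisons for efficacy, safety and pharmacokinetics do not use duration in this form and are unaffected. This is a correction worth making before the tables are programmed, not a threat to the trial's conclusions.

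**What to change.** Change SAP 16.4.1 and let 16.4.2 inherit it, per assay and using the derived nAb results:

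1. Derive duration only for participants with at least one positive post-baseline result. Report pre-existing positives with no later positive as a count, without a duration.
2. Censor at the last valid sample every participant whose last valid sample is positive, on or off treatment, and summarise duration by Kaplan-Meier with the number censored. Naming the method matters: under plain descriptive statistics, even the existing censoring rule has no defined effect.

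The cost is two sentences and a small programming change, with no new data. The drawback is that in small subgroups the median may not be reached, or may be unstable where few participants remain at risk.

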		
Censoring rules (details provided in body text):
 
 
- No event (PD or death)
 
- No baseline and/or post-baseline assessment
 
- Start of new anticancer treatment
 
- Event after two or more subsequent missing response assessments
 

Sensitivity Analysis 1: PFS counting all events (PD and death) regardless of the start of a new anticancer therapy and ignoring the number of missing evaluable tumor assessments before progression or death

Sensitivity Analysis 2: PFS as assessed by the Investigator

**Progression-Free Survival (PFS)** time is defined as the time from first administration of study treatment until the first documentation of progression of disease (PD) or death due to any cause, whichever occur first.

PFS = (date of PD or death or censoring – date of first administration of study treatment + 1)/30.4375 (months).

The following censoring rules will also be applied for the PFS computation:

- Participants with no event (PD or death) will be censored on the date of the last adequate tumor assessment
- Participants who do not have a baseline tumor assessment or who do not have any evaluable post-baseline tumor assessments will be censored at the date of first administration of study treatment unless death occurred on or before the time of the second planned tumor assessment (i.e. 16 weeks) in which case the death will be considered an event.
- Participants who start new anticancer treatment prior to an event will be censored on the date of the last evaluable tumor assessment before anticancer therapy is given.

Note: any systemic anticancer therapy, any anticancer surgery and any anticancer radiotherapy with exception of palliative bone radiotherapy will be considered as new/subsequent anticancer therapy and will lead to censoring.

- Participants with an event after two or more subsequent missing response assessments (i.e. no assessments in 112 days during the first 12 months of follow-up or 168 days after the first 12 months of follow-up) will be censored on the date of the last evaluable tumor assessment.

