#### 14.4.2 Subgroup analysis for PFS

PFS according to RECIST 1.1 as adjudicated by IRC will also be evaluated on all subgroups as defined in Section 8.2. This will be repeated for Japanese participants including only the ADA and nAb status subgroup.

For the ADA and nAb subgroups, participant listings will provide the following information: participant ID, age, sex, race, ADA status, nAb PD-L1 assay status, nAb TGF- $\beta$  assay status, date of first administration, date of last tumor assessment, date of event/censoring, event/censoring reason, time to event. Two listings will be created: for the ADA positive participants and for nAb positive in either assay (PD-L1 and TGF- $\beta$ ) participants.

Participants with missing subgroup category will not be included in the related subgroup analysis. Those subgroups analyses will be supported by Kaplan-Meir and forest plots (based on PFS rates at 6-month and 12-month).

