## 14.8 Overall survival

Analysis (Analysis Population)	Derivation	Statistical Analysis Methods	Missing data handling
Secondary endpoint: Overall Response (OS)			
Secondary analysis (ITT)	Time from first administration of study treatment to the date of death due to any cause	Kaplan-Meier estimates (product-limit estimates) will be presented together with a summary of associated statistics (median time, 3-, 6-, 9-, 12-, 24-month rate estimates) including the corresponding two-sided 95% confidence intervals. The confidence intervals for the median will be calculated according to Brookmeyer and Crowley (1982) and confidence intervals for the survival function estimates at above defined timepoints will be derived using the log-log transformation according to Kalbfleisch and Prentice (2011) (conftype=loglog default option in SAS Proc LIFETEST). The estimate of the standard error will be computed using Greenwood's formula.	
For alive participants, OS will be censored at last date known to be alive
 
The following dates will be considered to determine the last date known to be alive (dates past the data cut-off will be ignored by the derivation; details provided in body text):
 

• All participant assessment dates

• Start and end dates of anticancer therapies administered after study treatment discontinuation.

• AE start and end dates

• Last known alive date collected on the 'Subject Status / Survival Follow-Up' eCRF page (do not use follow up date)

• Study drug start and end dates

 
Date of discontinuation from the "Study Termination" eCRF page (do not use if reason for discontinuation is lost to follow-up or death)

**Overall survival (OS)** is defined as the time from first administration of study treatment to the date of death due to any cause:

OS = (date of event or censoring – date of the first dose + 1)/30.4375 (months).

For participants alive at the time of data cut-off date or who are lost to follow up, OS will be censored at the last date known to be alive. The date of event / censoring is defined in [Table 6](#).

**Table 6** Survival Event / Censoring

Survival Status	Date of event/censoring	Censoring
Participants alive or lost to follow-up before or at cut-off date	Last date known to be alive	Yes
Participants who died before or at cut-off date	Date of death	No

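### PFS and OS by ever/never ADA or nAb status, timed from first dose, build in immortal time that favours antibody-positive participants

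*SAP*

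**What the plan says.** SAP 16.4.1 announces an evaluation of whether ADA affects efficacy, naming PFS and OS, and sets the comparison: "Potential effect of ADA on safety, efficacy and PK will be evaluated on ADA positive status (ever positive, never positive". SAP 16.4.2 repeats this for nAb, positive in either assay.

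- **Status.** Table 10 defines ever positive as "At least one positive result at any time point, including baseline". The samples that count are wide: "samples collected during and after the on-treatment period (e.g. safety follow-up) including the ones collected during the re-initiation period will be included".
- **Clock.** PFS (14.4) is the "time from first administration of study treatment until the first documentation of progression of disease (PD) or death due to any cause". OS (14.8) is "Time from first administration of study treatment to the date of death due to any cause".
- **Display.** SAP 8.2 lists ADA and nAb status among the subgroups, run once 3 participants are ever positive. SAP 14.4.2 supports the PFS subgroups with Kaplan-Meier curves and "forest plots (based on PFS rates at 6-month and 12-month"); 14.8.1 does the same for OS. Both are repeated for Japanese participants.
- **Timing.** The SAP derives an onset date: "the date of the first assessment with positive ADA result will be considered as start date of ADA response". For PK, 16.1.2 orders trough concentrations by day relative to seroconversion. Nothing comparable is given for PFS or OS, whose listings hold "date of first administration, date of last tumor assessment, date of event/censoring, event/censoring reason, time to event" but no first-positive date.

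**The concern.** Treatment-emergent positivity is fixed by something that happens after time zero. To be classed as ever positive a participant must still be alive and sampled when the antibody is detected, and all the time before that sample is then counted as positive time. Early deaths have little chance to enter the ever-positive group and fall into the never-positive group. Longer treatment also brings more samples in which to turn positive.

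The bias has a known direction: it makes antibody-positive participants look better. The question the analysis is meant to answer is whether antibodies reduce efficacy, so this is the unsafe direction. SAP 4 says planned analyses may go into regulatory submissions or manuscripts, and a reader of a forest plot cannot see the problem.

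**Working it through.** **1. The plan's own figures.** The documents give no figure for this comparison and no ADA incidence or onset time. Their one design figure is the power of the ORR test. With N = 141, rejection at 22 or more responders, ORR 10% against 18%, the exact one-sided alpha is 0.0239 and the power 80.07%. It reproduces the stated 80% and is not touched by this point.

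**2. Chances to turn positive.** Protocol Table 2 has post-baseline ADA samples at D15, D29, D43 and D85, then every 6 weeks to W25, then every 12 weeks.

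| Treated to | On-treatment samples | With 2-3 end-of-treatment and follow-up samples |
|---|---|---|
| Week 9 | 3 | 5-6 |
| Week 25 | 6 (adds W13, W19, W25) | 8-9 |
| Week 49 | 8 (adds W37, W49) | 10-11 |

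The follow-up count is a range because the extracted table row shows two marks for three columns.

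**3. Guaranteed survival by hand.** Assume a constant hazard with median OS 9 months (9 × 30.4375 = 273.9 days) and no antibody effect. Six months is 182.6 days, so unconditional 6-month OS is 2^(-182.6/273.9) = 63%. For someone first positive t days after first dose it is 2^(-(182.6 - t)/273.9):

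| First positive | t (days) | 6-month OS |
|---|---|---|
| D15 | 14 | 65% |
| D43 | 42 | 70% |
| D85 | 84 | 78% |
| W25 | 168 | 96% |

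The gap over 63% comes from the definition alone and grows with later onset.

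**4. Simulated trials.** N = 141, 800 trials per scenario, 648 scenarios with no effect and 648 with a true HR of 1.3 after onset. All inputs except the visit schedules are assumptions:

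- 10, 20 or 40% prone to seroconvert, with onset uniform to Week 7, 19 or 37.
- Latent PFS median 6 or 10 weeks, dated at the next scan (every 8 weeks to 12 months, then every 12).
- 20% of first events in non-responders are deaths; 0 or 15% long responders.
- Post-progression survival median 12, 18 or 26 weeks, giving overall median OS of 20-43 weeks.
- 0 or 30% treated beyond progression; at least 15 months' follow-up.

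Ever minus never positive, percentage points:

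| Onset window | True effect | OS 6 mo | PFS 6 mo | OS 12 mo | PFS 12 mo |
|---|---|---|---|---|---|
| Weeks 1-7 | none | +2 to +8 | 0 to +2 | 0 to +4 | 0 to +1 |
| Weeks 1-19 | none | +10 to +23 | +1 to +10 | +3 to +12 | 0 to +4 |
| Weeks 1-37 | none | +16 to +30 | +4 to +25 | +5 to +19 | 0 to +10 |
| Weeks 1-7 | HR 1.3 | -9 to -1 | -7 to -2 | -10 to -4 | -3 to 0 |
| Weeks 1-19 | HR 1.3 | +1 to +16 | -3 to +5 | -6 to +3 | -2 to +2 |
| Weeks 1-37 | HR 1.3 | +9 to +25 | +2 to +20 | -1 to +12 | -1 to +8 |

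With no effect, the 6-month differences were above zero in all 648 scenarios. Positivity at baseline only gave -1 to +1. In the three windows 0%, 18-42% and 23-54% of ever-positive participants first tested positive on or after their own PFS event, which is why the PFS bias is smaller. Other runs on similar inputs reached 6-month OS of +10, +25 and +33, so these ranges are not bounds.

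**5. Hazard-ratio check.** The SAP plans no hazard ratio; this only shows cause and cure. A differently built null simulation (60,000 participants per scenario, 30% prone) gave these HRs for ever against never from first dose:

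| Positivity first detectable | PFS | OS |
|---|---|---|
| D15 | 0.93-0.97 | 0.92-0.96 |
| D43 | 0.81-0.90 | 0.79-0.86 |
| D85 | 0.53-0.82 | 0.66-0.76 |
| W25 | 0.37-0.50 | 0.54-0.62 |

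With status switching at the first positive sample, the OS HR was 0.97-1.03 throughout. At N = 141, time-dependent status gave null medians of 0.95-1.07 (PFS) and 0.96-1.06 (OS) where at least 10% were ever positive, and 0.93-1.10 and 0.90-1.10 over all scenarios.

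**6. Precision.** The 95% half-width of a 6-month OS difference is 1.96 × sqrt(S(1 - S)(1/n + 1/(141 - n))), with S 50-60%. For n = 7, 14, 28 and 42 ever-positive participants it is about 38, 28, 21 and 18 points. The null OS bias is 0.1-0.5 of the half-width with onset in Weeks 1-7, 0.4-1.4 in Weeks 1-19 and 0.5-1.7 in Weeks 1-37.

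**The case against.** The strongest reply is that little rests on this comparison. SAP 8.2 says the study is not powered for subgroups, no between-group test or hazard ratio is planned, and the primary ORR analysis is untouched. Timing is partly visible: time to first positive is summarised, pre-existing and treatment-emergent positivity are tabulated separately, and the 16.4.1 and 16.4.2 listings give the first-positive date by participant. If onset proves early, the bias is small. For PFS the immortal time is only partial, since samples after progression count. With few positives, sampling error exceeds the bias and a time-dependent estimate is itself imprecise.

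All of that is true, and it limits the severity. It does not remove the point. The SAP calls the comparison an evaluation of effect; a descriptive curve with a known direction of error still misleads; imprecision does not cancel a systematic shift; and separate listings leave the curves uncorrected.

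The simulations also omit two features of the plan. They do not apply the PFS censoring for new anticancer therapy or for two or more missed assessments, and they assume follow-up that makes 12-month rates fully observed, which the 9-month primary cut-off does not guarantee. These affect the illustrative sizes, not the mechanism.

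**Conclusion.** The concern holds, and the plan should be changed. For OS the immortal time is strict for every treatment-emergent participant; for PFS it is partial. Participants positive at baseline carry none and dilute it. DOR is outside this point.

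The size cannot be known from the documents. Under the assumptions above it is minor if antibodies appear within about 7 weeks, and can match or exceed sampling error if onset extends to 19 or 37 weeks. A true harm of HR 1.3 stays visible at both time points with early onset. With later onset it can be hidden at 6 months; at 12 months it is then often visible or neutral, and is mostly hidden only when onset is late. Confidence in the direction is high; in any particular figure it is moderate at best.

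**What to change.** In SAP 14.4.2, 14.8.1, 16.4.1 and 16.4.2:

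- Base any statement about an ADA or nAb effect on PFS or OS on a model with antibody status as a time-dependent covariate switching at the first positive sample, reported with its 95% CI. For nAb in either assay, use the earlier date, as 16.1.2 does for PK.
- Show pre-existing positives separately. If curves are wanted, use Simon-Makuch curves.
- If ever/never PFS and OS displays stay, label them descriptive and not evidence of an antibody effect.
- Add the first-positive date to the PFS and OS listings. Where positives are very few (for example fewer than 10, or in the Japanese repeats), give listings only.
- Keep ever/never status for immunogenicity incidence.

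The cost is SAP wording and a start-stop dataset built from dates already derived. The estimate will be imprecise: its 95% CI spans a factor of about 4.1 (PFS) and 3.2 (OS) either side with 3 ever-positive participants, 2.7 and 2.3 with 7, and 1.6 for both with about 28. Scan dating also dilutes PFS: a true HR of 1.3 appears as 1.07-1.31, so a null PFS result should not be read as no harm.

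A Day 43 landmark is optional. For PFS it drops about 6-10% if progression is dated at the first planned scan, or 1 - 2^(-6/median) = 27-41% if events occur continuously with a median of 13 or 8 weeks. It would class 54-77% of ever-positive participants as negative when onset runs past Week 7; both losses should be reported if it is used.
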